RIOT	return to intended oncological treatment
TC	Total Cardiology

PROTOCOL SYNOPSIS

TITLE	Trimodal prehabilitation for cystectomy patients to enhance post-operative care: A randomized control trial
VERSION	1.0
STUDY DESIGN	Pragmatic RCT with assessor blinding
STUDY	52 weeks
STUDY CENTRES	Single Centre Trial (Rockyview General Hospital, Calgary, AB)
PRIMARY OBJECTIVE	To investigate the effects of a trimodal 8-week prehabilitation program on the return to function of patients undergoing RC as measured by six-minute walk test (6MWT) and walking speed, as well as on traditional clinical outcome measures including length of hospital stay, rates of morbidity, and return to oncological treatment.
SECONDARY OBJECTIVES	
To investigate the impact and patient acceptability of a trimodal 8-week prehabilitation program on patient satisfaction and quality of life, as determined through questionnaires, and patient interviews
 
To investigate the effects of a trimodal 8-week program on traditional outcomes including length of hospital stay, rates of morbidity, and return to oncological treatment
 
To establish appropriate criteria that effectively identifies and triages those patients who would benefit most from prehabilitation
 
To evaluate which functional outcome measures represent a valid index of recovery and are sensitive to change.

NUMBER OF PARTICIPANTS	50
DIAGNOSIS AND MAIN INCLUSION CRITERIA	
Inclusion Criteria:
 
 1. Male or female ≥ 18 years of age at time of consent for surgery. 2. Documentation of bladder cancer diagnosis as evidenced by diagnostic imaging and biopsy. 3. May or may not receive adjuvant therapy. 4. Written informed consent obtained from subject 
Exclusion Criteria:
 
 1. Presence of a condition or abnormality that in the opinion of the

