1.2 Background

In 2017 an estimated 8,900 Canadians will be diagnosed with bladder cancer¹. The mainstay of surgical treatment for muscle-invasive bladder cancer is radical cystectomy (RC) with lymph node dissection. Large prospective cohort studies suggest that at least 64% of patients undergoing RC experience at least one complication within 3 months^{2,3}. In an attempt to reduce

these complications and shorten length of hospital stay postoperatively, Rockyview General Hospital (RGH) is implementing a new enhanced recovery protocol (ERP) that will employ multidisciplinary, evidence-based clinical interventions, drawing upon the Enhanced Recovery After Surgery (ERAS) protocols⁴ for its development. ERAS protocols have been shown to reduce length of hospital stay and morbidity post-colorectal surgery, and provide an evidence-based, multidisciplinary approach to surgical care. It is unclear whether available evidence suggests ERPs facilitate earlier recovery of strength and function, and previous efforts to improve recovery have traditionally focused on the postoperative period, during which cancer patients may be fatigued, concerned about disturbing the healing process, or anxious as they await additional treatments for their underlying condition.⁵ Given this, the preoperative period may in fact be a more salient time to intervene. Optimizing an individual's functional capacity can begin during the waiting period before surgery as it capitalizes on the better physical health compared with the acute postoperative period^{6,7}. Moreover, interventions prior to surgery can potentially improve complication rates perioperatively. This process of enhancing an individual's functional capacity to withstand the stress of surgery is called prehabilitation⁸.

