3.3 Secondary Objectives

- To investigate the impact and patient acceptability of a trimodal 8-week prehabilitation program on patient satisfaction and quality of life, as determined through questionnaires and patient interviews.
- To investigate the effects of a trimodal 8-week program on traditional outcomes including length of hospital stay, rates of morbidity, and return to oncological treatment
- To establish appropriate criteria that effectively identifies and triages those patients who would benefit most from prehabilitation, so that efficient health care service can be made accessible to those who need it most.
- To evaluate which functional outcome measures represent a valid index of recovery and are sensitive to change.

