4.5 Total Number of Participants and Sample Size Justification

A total of 50 participants who meet the inclusion criteria and are willing to participate in the study will be enrolled, with 25 participants randomly allocated to each study treatment group. As this is a pilot study, we have funding for at most 25 participants to undergo prehabilitation.

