5.3 Method of Assigning Subjects to Treatment Groups

Up to 50 eligible patients will be randomly assigned to the two groups in a 1:1 ratio using a computer-generated randomization process whereby brown sealed envelopes will be prepared and opened after the patient's consent has been signed.

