6.9 Traditional/Clinical Outcomes

Clinical outcomes to be used in this study will include length of hospital stay, 30d readmission rate, return to intended oncological treatment (RIOT), and postoperative complications classified according to Clavien-Dindo classification. Data is collected prospectively.

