9 STATISTICAL METHODS AND CONSIDERATIONS

9.1 Quantitative Analysis

An available case analysis without imputation of missing values will be conducted. All analyses will be performed using Stata 14.1 (2015, StataCorp). All continuous variables will be reported as mean, 95% confidence interval. Categorical variables will be presented as frequency (%) and compared using Pearson's χ^2 test. A mixed effects model will be used to analyze repeated measures, including our primary outcome the 6MWT, because this method had advantages in dealing with missing data and controlling for baseline variables. A P-value <0.05 will be considered statistically significant.

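### Pearson's chi-square is fixed for every categorical variable, so if the ordered Clavien-Dindo grades are compared as recorded, the test ignores their order in a sparse table

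*Protocol*

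**What the plan says.** Section 9.1 sets one rule for categorical data: "Categorical variables will be presented as frequency (%) and compared using" Pearson's chi-square test. The statistics entry of the synopsis repeats it. Neither place makes an exception for ordered categories or small expected counts. The mixed model is reserved for repeated measures, so it does not cover complications. The threshold is "A P-value <0.05 will be considered statistically significant".

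Section 6.9 lists the clinical outcomes, among them "postoperative complications classified according to Clavien-Dindo classification". It gives no cut point, no definition of a major complication, and no statement of whether the highest grade per patient is used.

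The objectives use looser words. Section 3.3 places "traditional outcomes including length of hospital stay, rates of morbidity, and return to oncological treatment" among the secondary objectives. The synopsis lists the same items under both its primary and its secondary objectives. Section 9.1 names the 6MWT as the primary outcome.

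Section 4.5 fixes the size, "with 25 participants randomly allocated to each study treatment group", and sections 4.5 and 9.2 attribute it to the funding available.

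**The concern.** Clavien-Dindo grades run from no complication to death. Pearson's chi-square treats such grades as unordered labels: exchanging the columns for grade I and grade IV leaves the statistic unchanged. It also spreads the comparison over one degree of freedom per column less one, so five for grades 0 to V, and seven if III and IV are split into a and b.

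At 25 per arm the higher grades will hold very few patients. The chi-square approximation is then poor, and a general move toward milder complications is hard to detect. The p-value also gives neither the direction nor the size of an effect. That matters because section 2 intends the results as the basis for possible multi-site studies.

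The protocol is not silent on the test; it selects one. A later analysis plan that used an ordinal method would depart from section 9.1.

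**Working it through.** **No figure to reproduce.** The protocol states no power, effect size or grade distribution for this outcome. The check compares two tests on the same simulated data.

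**Inputs from the protocol**
- 25 per arm (section 4.5), "randomly assigned to the two groups in a 1:1 ratio" (section 5.3).
- Significance level 0.05 (section 9.1). Sidedness is not stated; two-sided is assumed.
- Any-complication risk 64%, from section 1.2: "at least 64% of patients undergoing RC experience at least one complication within 3 months". Used as the control risk, it leaves 36% with grade 0.

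**Assumed inputs**
- Control grades 0, I, II, III, IV, V: 36%, 14%, 30%, 13%, 5%, 2%.
- A proportional-odds shift: every cumulative odds is multiplied by the same odds ratio (OR).

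**Shift.** For cumulative probability c, the treated value is c' = OR × c/(1 − c) ÷ [1 + OR × c/(1 − c)]. For grade 0, 0.36/0.64 = 0.5625. At OR 2, 1.125/2.125 = 0.53. At OR 3, 1.6875/2.6875 = 0.63.

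**Sparsity.** Expected counts per arm under the control distribution are 25 × p = 9, 3.5, 7.5, 3.25, 1.25 and 0.5. Four of the six grades fall below 5.

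**Tests.**
- Pearson: X² = Σ(O − E)²/E over non-empty columns, no continuity correction.
- Wilcoxon, with column totals t, midranks m and counts a in one arm: W = Σ a·m; E(W) = 25 × 51/2 = 637.5; V = (25 × 25/12) × [51 − Σ(t³ − t)/(50 × 49)]; z = (W − E(W))/√V.

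Each scenario has 6,000 simulated trials, so the Monte Carlo standard error is at most √(0.25/6000) = 0.6 percentage points.

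**Power under a consistent shift (chi-square / rank-sum)**

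| Levels compared | OR 2 | OR 3 | OR 5 |
|---|---|---|---|
| Eight (III and IV split) | 8.6% / 25.8% | 21.2% / 53.0% | 48.3% / 81.9% |
| Six (0 to V) | 11.4% / 25.1% | 27.9% / 53.1% | 54.8% / 81.2% |
| Four (0, I–II, III, IV–V) | 13.5% / 24.5% | 33.6% / 51.7% | 62.9% / 81.7% |
| Three (0, I–II, III–V) | 18.1% / 24.9% | 41.6% / 51.1% | 70.4% / 80.7% |

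For six levels, chi-square keeps 0.46, 0.45 and 0.52 of the rank-sum power at OR 2, 2.5 and 3, and 0.61 and 0.67 at OR 4 and 5. A second assumed spread (36%, 16%, 25%, 14%, 6%, 3%) gives nearly the same: 11% against 25% at OR 2, and 26% against 53% at OR 3.

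**Yes/no instead of grades.** Chi-square on any complication versus none, in the same six-level data, has 24.9%, 53.3% and 81.3% power at OR 2, 3 and 5. That equals the rank-sum test.

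**Under no effect.** Chi-square rejects 3.2% of the time with six levels and 2.4% with eight; the rank-sum test rejects 4.8% and 4.9%. The sparse table makes chi-square conservative, which explains part of its lost power.

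**Effects that are not a consistent shift (six levels, chi-square / rank-sum)**
- Only severe grades fall: 21% / 14%.
- All grades III to V become grade I: 40% / 23%.
- Most of grade II becomes grade I: 62% / 13%.
- Most of grade II becomes no complication: 42% / 31%.
- Complications of every grade become less frequent in about equal proportion: 33% / 50%.

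Chi-square is ahead in four of these five patterns.

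**The case against.** The strongest reply is that the protocol never says the grades themselves are tested. Section 6.9 says how complications are classified, and the objectives speak of rates. A rate is naturally a proportion, for which Pearson's chi-square is conventional and, on the figures above, loses nothing. This stands, and it makes the point conditional. It does not remove it: the only operational description of the outcome is the grade, no cut is named, and any-versus-none and severe-versus-not are different outcomes. When only severe grades fall, an any/none comparison rejects just 5.7% of the time.

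A second reply is that deriving a secondary outcome belongs in the analysis plan. That is fair for the derivation. It is weaker for the test, which section 9.1 already fixes without exception.

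A third is that the rank test is not uniformly better. This also stands: its advantage depends on a broadly consistent shift across grades.

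A fourth is that the stakes are small. Section 9.1 makes the 6MWT primary, sections 3.2 and 3.3 place morbidity among the secondary objectives, and funding set the size. The rank test itself has only 25% to 53% power at OR 2 to 3. All of this stands and limits the weight of the point.

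**Conclusion.** The point holds conditionally. If Clavien-Dindo grades are compared as recorded, the named test ignores their order in a sparse table. Under the assumed six-level distribution and a proportional-odds shift of OR 2 to 3, it has about half the power of a rank-sum test. Over all the proportional-odds scenarios run, the share of power lost ranges from 13% (three levels, OR 5) to 67% (eight levels, OR 2). It is nil for an any/none rate, and the ranking reverses for some effects confined to certain grades.

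Three stronger readings are tempting, and the protocol does not support them:
- That the trial will compare unordered grades and lose half its power outright. No section says a full grade table is tested, and only the 64% figure in the calculation comes from the protocol.
- That sparse tables raise the false-positive risk for this outcome. In the simulation, chi-square rejected less often than 5%.
- That a primary analysis is damaged. The synopsis does list morbidity under its primary objective, but sections 3.2, 3.3 and 9.1 make it secondary to the 6MWT.

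What remains is an inexpensive improvement to a secondary analysis of a pilot.

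**What to change.** In section 9.1 and the synopsis, keep Pearson's chi-square for binary and nominal variables, and add: The highest Clavien-Dindo grade per patient (0 to V) will be compared between groups with the Wilcoxon rank-sum test, with a proportional-odds common odds ratio and its 95% confidence interval.

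This settles which quantity is analysed and adds a direction and an effect size that a later trial can use. If the investigators intend a yes/no rate instead, stating the cut in section 6.9 before data are seen would make Pearson's test suitable as it stands.

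The cost is one sentence in two places, with no new data, visits or patients. There are two small downsides: the common odds ratio assumes proportional odds, and the rank test is less sensitive to an effect confined to severe grades. Reporting the frequency of each grade by arm, as section 9.1 already provides, lets readers see such a pattern. The change does not make the pilot well powered for morbidity.

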9.2 Power & Sample Size

Power and sample size are limited by the amount of funding available. The grant amount of \$15,000 allows for a total of ~50 patients with 25 being enrolled in the prehabilitation group.

10 DATA COLLECTION, RETENTION AND MONITORING

10.1 Data Collection

All data collected will be anonymized with a locked, password-protected file (available only to the primary investigator) identifying participants to their anonymized data. The research member responsible for statistical analysis will be provided with anonymized data only. Collection will be completed at multiple timepoints as outlined in this document and will be obtained from direct patient interactions, Alberta Health Service's Discharge Abstract Database (DAD), National Surgical Quality Improvement Program (NSQIP) data, and Sunrise Clinical Manager (SCM).

Aside from the clinical data obtained from these sources, qualitative interviews will be completed following the study where participants are invited to talk about their experiences with prehabilitation. Their responses will be anonymized and all direct and indirect identifying information will be redacted prior to analysis by the research team.

Participants will be informed regarding the limits of confidentiality and that all efforts will be made to ensure their clinical data and interview responses are anonymized and kept confidential.

10.2 Data Identifiers

Personal identifiers that we will be collecting include:

- Surname, first name, and initials;
- Address and full postal code;
- Telephone number and email address;
- Full date of birth and age at time of collection;
- Health Care Number;
- Hospital admission and discharge date;

This information will be collected to allow the research team to contact the research participants in order to provide information regarding the study, and to schedule appointments specific to the study. Clinical outcomes such as length of stay are necessary to determine the effectiveness of our intervention.

The researcher responsible for collecting this information and assessing the patients will not be blinded to the patient's treatment group. Their responsibility includes anonymizing all collected data that is to be analyzed statistically. A password-protected spreadsheet will be created that links an anonymous identifier to the above identifying information. A second member of the team, blinded to this process, will be responsible for analyzing the anonymized data statistically.

Once data collection is complete and interviews are completed, all master lists that link identifiers with the anonymized data will be securely deleted.

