4 STUDY DESIGN

4.1 Study Overview

This is a single center, single-blind, pragmatic randomized-control trial. There will be a total of 50 (fifty) participants in the study. Each participant will be randomly enrolled into a prehabilitation or no-prehabilitation group at time of consent for RC and those in the intervention group will undergo 8 weeks of prehabilitation through the Total Cardiology program, hosted through the Repsol Centre. Each participant, independent of study group assignment, will receive the standard treatment as outlined in the Enhanced Recovery Protocol (ERP) for Radical Cystectomies (see Appendix 1). Those enrolled in the prehabilitation group will attend 2 supervised exercise-based sessions per week and will complete a home-exercise program three times per week (total 5 exercise sessions per week). In addition, they will receive 5 protein supplement drinks per week to consume after exercise, and will attend classes on nutrition and stress/anxiety reduction techniques. Measurements will be taken at baseline, 6 weeks (as a part of their regularly scheduled pre-admission clinic appointment), 8 weeks (just prior to surgery), 4 weeks post-op, and 8 weeks post-op.

Those patients enrolled in the no-prehabilitation group will receive a general, unsupervised, home-exercise program, information regarding good nutrition. They will be followed at their regularly scheduled appointments. Again, measurements will be taken at the same time intervals as the prehabilitation group.

Screening data will be reviewed to determine subject eligibility. Subjects who meet all inclusion criteria and none of the exclusion criteria will be entered into the study.

The following treatment groups will be established:

- Standard ERP + Trimodal Prehabilitation
- Standard ERP

Total duration of subject participation will be approximately sixteen weeks. Total duration of the study is expected to be approximately 1.5 years.

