5.4 Blinding

Due to the nature of the study, we are unable to conceal to the research staff or participants from the different aspects of trimodal prehabilitation. However, all research data will be coded with anonymous unique identifiers so statistical analysis is performed blinded and without bias. The assessor-blinded data will not be broken on completion of the clinical study.

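### The synopsis and section 5.4 claim assessor blinding, but section 10.2 says the person assessing patients is not blinded; only the analyst is

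*Protocol*

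**What the plan says.** All the relevant statements are in the protocol.

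- **Synopsis, study design:** "Pragmatic RCT with assessor blinding".
- **4.1 Study Overview:** "This is a single center, single-blind, pragmatic randomized-control trial". It does not say who is blinded.
- **5.4 Blinding:** the section opens by conceding that "we are unable to conceal to the research staff or participants from the different aspects of trimodal prehabilitation". It then says data are coded with anonymous identifiers "so statistical analysis is performed blinded and without bias". It closes with "The assessor-blinded data will not be broken on completion of the clinical study".
- **10.2 Data Identifiers:** "The researcher responsible for collecting this information and assessing the patients will not be blinded" to the patient's group. Of the same researcher it adds: "Their responsibility includes anonymizing all collected data that is to be analyzed statistically". It then separates off the analyst: "A second member of the team, blinded to this process, will be responsible for analyzing the anonymized data statistically".
- **10.1 Data Collection:** the person doing the statistics receives anonymized data only.

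The functional tests in 6.7 are scheduled at Visits 1, 3, 4 and 5 (7.1, 7.3, 7.4, 7.5). None of these sections says who runs the tests. Step 6 of 4.6 gives later physical assessments to a physiotherapist, without saying whether that person knows the allocation.

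**The concern.** A reader of the synopsis will take assessor blinding to mean that whoever measures the outcomes does not know the group. The body of the protocol says that person does know.

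The abstract (1.1) puts the main outcome at the eighth postoperative week, measured by the 6MWT, and 9.1 names the 6MWT as primary. Section 6.7 describes a test in which the participant covers as much distance as possible in the time allowed. A tester who knows the group can influence encouragement and recording, even unintentionally. Coding the data afterwards protects choices made in the analysis; it cannot undo anything that happened during measurement. The label thus credits the primary outcome with protection against detection bias that the plan does not supply. Section 2 says the results are meant to support multi-site studies and further funding applications, so a wrong design label would carry forward.

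**Working it through.** The protocol gives no figure to reproduce. The check is a comparison of statements, followed by a count of the measurements affected.

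**Step 1. Who is blinded, by role**

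| Role | Status | Where |
|---|---|---|
| Participants | not blinded | 5.4, first sentence |
| Research staff | not blinded, no exception for testers | 5.4, first sentence |
| Researcher assessing patients | not blinded | 10.2 |
| Analyst | blinded | 5.4, 10.1, 10.2 |
| Outcome tester at Visits 3, 4, 5 | not named, no blinding stated | 7.3, 7.4, 7.5 |

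Assessor blinding is asserted twice (synopsis; last sentence of 5.4). It is denied directly in 10.2 and undercut by the first sentence of 5.4. The synopsis and 10.2 cannot both stand.

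**Step 2. Does 10.2 cover the outcome tests?** The protocol does not name the tester at Visits 3 to 5, so an unblinded tester there is an inference. It rests on three points:

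1. 10.2 speaks of assessing the patients without restriction and gives the same researcher all collected data to anonymize, so the role goes beyond handling identifiers.
2. 5.4 makes no exception for a tester.
3. The physiotherapist in 4.6 is not said to be blinded.

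**Step 3. Which measurements are exposed?** Inputs: 4 functional tests (6.7: 6MWT, 10-metre walk, sit-to-stand, hand grip); 4 visits with testing (7.1 step 7, 7.3 step 3, 7.4 step 2, 7.5 step 2; none in 7.2); randomization at 7.1 step 9, after the baseline tests; 50 participants (4.5).

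- Tests per participant: 4 × 4 = 16
- After randomization: 4 × 3 = 12, and 12/16 = 75%
- All participants: 16 × 50 = 800 tests, of which 12 × 50 = 600 follow randomization
- 6MWTs after randomization: 3 × 50 = 150
- Week-8 6MWTs: 1 × 50 = 50

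The 50 baseline sets are unaffected, since allocation does not yet exist. The counts assume full attendance and are upper limits: 7.2 withdraws patients found to be poor surgical candidates, and 8.1 does not replace withdrawals. They show how much measurement the label covers, not the size of any bias.

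**The case against.** The best defence is that *assessor* was meant as the person who evaluates the coded data. In 5.4 the closing sentence directly follows the one on coded data for analysis. Read that way, 5.4, 10.1, 10.2 and the single-blind label in 4.1 all agree, and the fault is a misused term. This reading is possible for 5.4, which makes that section the less secure of the two claims. It does not rescue the synopsis, where the phrase stands alone and will be read in its ordinary sense. Section 10.2 itself keeps the person assessing patients apart from the person analysing data. Even if this was the intent, the wording has to change.

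Three further points are fair. The first sentence of 5.4 is general and does not mention testers, so the direct contradiction rests on 10.2. The visit sections name no performer for any procedure, so their silence is weak evidence; that is why the unblinded tester is put forward only as an inference. And this is a pilot limited by funding, in which an unblinded tester may be a reasonable choice. None of these lets the synopsis and 10.2 both be true.

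Two phrases are not further contradictions: *single-blind* in 4.1 can be true of the analyst, and *without bias* in 5.4 qualifies the statistical analysis. Both need only clarification. The matter is also not one to leave to a statistical analysis plan, because the conflict is between statements the protocol itself makes.

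**Conclusion.** The concern holds. The protocol claims a protection for its primary outcome that its own text denies, and this must be corrected. The contradiction depends on no numerical assumption and would remain even if the Visit 3 to 5 tester turned out to be someone else. What rests on inference is only that the tests after randomization, three quarters of those scheduled, are run by someone who knows the group. The documents do not allow the resulting bias to be sized.

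**What to change.** The sponsor should first confirm that 10.2 states what is intended. If it does:

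- **Synopsis and 5.4:** replace the assessor-blinding wording with: *participants, research staff and outcome assessors not blinded; statistical analyst blinded to group*. Check that group codes are masked in the analyst's file, since 10.1 and 10.2 speak only of anonymized data.
- **5.4:** delete the closing sentence on assessor-blinded data, and reduce the sentence on analysis to the fact that the analyst is blinded.
- **4.1:** say that single-blind refers to the analyst.
- **10.2:** leave unchanged.
- **Reporting:** do not describe the trial as assessor-blinded.

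The cost is a wording amendment in three places and a less favourable stated design.

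The label may stay only if an existing team member unaware of allocation will run the tests at Visits 3, 4 and 5. Then 5.4 and 10.2 must be rewritten to say so. Someone else must do the diary review at Visit 3 (7.3 step 1), because the diary shows protein supplement use (5.6). Since 5.6 has participants bring the diary to every visit, the tester should not see it at Visits 4 and 5 either. This route needs a separate tester for up to 3 × 50 = 150 sessions, and participants, who know their group, may still reveal it.
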